#### 4) Summary statistics for changes

With respect to CDRS-R total score at each evaluation time-point, and changes from baseline, summary statistics will be calculated for each treatment group. On the basis of the model used for the primary analysis, the estimated inter-group difference and 95% confidence interval, and the p-value, will be calculated for each evaluation time-point.

### 9.1.3 Primary endpoint subgroup analysis

Subgroup analyses will be performed with the below demographic factors. For each subgroup, an MMRM model will be applied, taking treatment group, observation time-points, and interaction between treatment group and observation time-points to be fixed effects; the baseline CDRS-R total score to be a covariate; and the covariance structure for error variance to be unstructured. The estimated difference between the duloxetine and placebo groups 6 weeks after initiation of administration, and the p-value, will thus be calculated. The degree of freedom will be adjusted using the approximation of Kenward and Roger.

- Age category (<12, ≥12)
- Sex (male, female)
- Baseline CDRS-R total score (up to 60, 61 or more)
- Baseline body weight (below the median for the entire FAS, above the median for the entire FAS)
- Depressive episode ordinal number (first time, second time or more)

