As explained above, in this study, the inter-group difference (placebo - duloxetine) between the duloxetine group and the placebo group in CDRS-R change up to week 6 of treatment period is assumed to be 5.9, the standard deviation in CDRS-R change is assumed to be 12.0 in both groups, and the effect size is predicted to be 0.49. It is thus estimated that 66 subjects per group (total: 132) are required to achieve a detection power of 80% or higher in a two-sample t-test at a two-sided significance level of 0.05. Therefore, predicting the dropout rate to be 10%, the target total number of subjects has been set at 148 (74 per group).

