### 4.2 Allocation method

The subjects whose eligibility is confirmed after completion of the screening period will be allocated to either the duloxetine or placebo group in a ratio of 1:1, by the stochastic minimization method, using age (<12, ≥12) and study site as allocation factors.

Consideration should be given so that the maximum inter-group difference at each study site does not exceed two subjects.

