### 6.2 Statistical tests

The level of significance for the statistical tests will be 0.05 (two-sided), unless stated otherwise. The

primary endpoint in this study will be only change in CDRS-R total score from baseline, and no analyses will be performed taking into consideration multiplicity concerning multiple items and multiple time-points.

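### SAP 9.1.3 estimates the treatment effect separately in each subgroup level but never compares the levels, so its p-values are likely to look discordant even when the effect is uniform

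*SAP*

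**What the plan says.** SAP 9.1.3 lists five factors, each with two levels: age category, sex, baseline CDRS-R total score, baseline body weight and episode number. It fits a separate MMRM in each level, which makes ten models. The fixed effects are treatment, visit and their interaction, with "the baseline CDRS-R total score to be a covariate" and no other covariate. The output is described in one sentence: "The estimated difference between the duloxetine and placebo groups 6 weeks after initiation of administration, and the p-value, will thus be calculated".

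Four other places matter for comparison:

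- SAP 9.1.1, the primary model, adjusts for age category as well as baseline score. SAP 4.2 allocates patients "using age (<12, ≥12) and study site as allocation factors".
- SAP 9.1.1, 9.1.2 item 4 and 9.2.1 each name a 95% confidence interval for their estimates. SAP 9.1.3 does not.
- SAP 6.2 sets the test level: "The level of significance for the statistical tests will be 0.05 (two-sided), unless stated otherwise". It makes no multiplicity adjustment.
- Protocol section 8 plans no subgroup analysis of efficacy, and no treatment-by-subgroup interaction appears in either document.

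**The concern.** A subgroup analysis asks whether the treatment effect differs between levels. The planned output does not answer that. It gives two p-values per factor, each testing whether the effect in one level is zero. A reader who finds one below 0.05 and the other above it may conclude that the drug works in one group and not in the other. With a trial sized for one overall comparison, each level has modest power, so such a pattern arises often by chance.

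The age factor is the likeliest to be read this way. Protocol section 1 notes that depressive symptoms change with developmental stage, and Protocol 3.2 reports different concentration ratios to adults at ages 7 to 11 and 12 to 17 (0.829 and 0.686). What is at stake is the interpretation of supplementary results, not the primary conclusion.

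**Working it through.** **Inputs from the documents.** Protocol 8.2: the group difference "in CDRS-R change up to week 6 of treatment period is assumed to be 5.9", and "the standard deviation in CDRS-R change is assumed to be 12.0 in both groups". SAP 6.2: two-sided 0.05. Protocol 8.2 also gives 4.66 as the difference in the overseas HMCL study, used here as a lower value. The documents give no subgroup shares, so splits from 50/50 to 20/80 are assumed.

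**Step 1: reproduce the plan's own figure.** The Protocol says: "It is thus estimated that 66 subjects per group (total: 132) are required to achieve a detection power of 80% or higher". The effect size is 5.9/12 = 0.49. Noncentral-t power is 0.7944 at 65 per group and 0.8005 at 66. Allowing for 10% dropout, 66/0.9 = 73.3, rounded up to 74 per group, or 148. The plan's figures are reproduced.

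**Step 2: power within a level.** With n patients per group in a level, the SE of the difference is 12 × √(2/n). At a 50/50 split n = 33, the SE is 2.95, the noncentrality is 5.9/2.95 = 2.00 and the power is 0.503. A week-6 t-test stands in for the MMRM.

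**Step 3: chance that exactly one level is significant when the true effect is the same in both.** The levels contain different patients, so the probability is pA(1 − pB) + pB(1 − pA).

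| Split | n per group in each level | Power at 5.9 | Exactly one significant, effect 5.9 | Exactly one significant, effect 4.66 |
|---|---|---|---|---|
| 50/50 | 33, 33 | 0.503, 0.503 | 0.500 | 0.450 |
| 40/60 | 26, 40 | 0.413, 0.584 | 0.515 | 0.457 |
| 30/70 | 20, 46 | 0.329, 0.645 | 0.550 | 0.474 |
| 25/75 | 16, 50 | 0.270, 0.682 | 0.584 | 0.491 |
| 20/80 | 13, 53 | 0.226, 0.708 | 0.614 | 0.506 |

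With 74 per group the range at 5.9 is 0.495 to 0.624. With no effect the probability is 2 × 0.05 × 0.95 = 0.095.

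**Step 4: at least one of five factors discordant.** The five factors divide the same patients, so their results are correlated and the per-factor figures cannot simply be multiplied. A simulation of 10,000 trials, with 66 per group and mutually independent factors, gives:

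- effect 5.9: 0.847 with all splits 50/50, and 0.898 with splits of 20, 30, 30, 50 and 20%;
- effect 4.66, all 50/50: 0.788;
- no effect, all 50/50: 0.291.

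**Step 5: the interaction test on the same footing.** Under a uniform effect it errs in 5% per factor. For at least one of five independent unadjusted tests the rate is 1 − 0.95⁵ = 0.226 (simulated 0.22). The figure to set against 85-90% is therefore about 23%, not 5%.

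**Step 6: what the interaction test can detect.** At 50/50 the SE of the difference between the two effects is √2 × 2.95 = 4.18 points. The difference in effects detectable with 80% power is (1.96 + 0.84) × 4.18 ≈ 11.7 points, about twice the assumed treatment effect. Power for a 5.9-point difference in effects is 0.292 at 50/50 and 0.227 at 25/75 (SE 4.87).

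**The case against.** The strongest reply is that separate models estimate each level's effect without bias, that the SAP sets no rule for comparing significance across levels, and that no decision rests on the subgroups. The discordance rates are then the error rate of a reading that the plan does not prescribe. This stands in part. A reader might infer that the analyses will show false subgroup differences, and the documents do not support that. The false impression needs someone to compare p-values, and even then it is a probability that falls to about 10% per factor if there is no effect. But the plan offers nothing else with which to compare the levels.

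Three other stronger readings also go too far.

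- **Age.** A reader might blame the missing age term for spurious differences. Age category is constant within the age subgroups and has to drop out there. In the other four factors its omission departs from the primary model and costs at most some precision.
- **Confidence intervals.** A reader might infer that none is planned. SAP Table 1 has a general output item that includes a 95% CI, and SAP section 1 leaves output details to separate mock tables. All that can be said is that the text of 9.1.3 does not name one.
- **Labelling.** Protocol section 1 speaks of an additional pediatric indication. Neither document says that the age subgroup will determine it.

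It is also fair to object that the interaction test is weak at this sample size. That is correct, and it is a reason to report intervals as well as the test.

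**Conclusion.** The point holds as a gap in how the subgroup results will be interpreted. SAP 9.1.3 contains no comparison of the treatment effect between levels, and its text names only a difference and a p-value. Under the design assumptions and a uniform effect, the p-values within a factor disagree in about 50-61% of trials, and at least one of five factors disagrees in about 85-90%. At an effect of 4.66 the figures are about 45-51% and 79%. With no effect they are about 10% and 29%. The primary estimate, its test and its alpha are untouched.

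These sizes rest on assumed subgroup shares, independent factors and a week-6 t-test in place of the MMRM. The per-factor result changes little across the splits tried.

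**What to change.** For each factor, fit one MMRM in the whole FAS with treatment x visit x subgroup and all lower-order terms, baseline CDRS-R and age category. Age category keeps the model consistent with the primary one and may gain precision; for the age factor it is already the subgroup term. From this model report:

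- the week-6 difference with 95% CI in each level;
- the between-level difference with 95% CI and the interaction p-value.

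Label the analyses exploratory. State that a non-significant interaction is not proof of a consistent effect, given power of about 29% for a 5.9-point difference in effects at 50/50 and about 23% at 25/75. Whether to keep the within-level p-values is a matter of preference once the between-level comparison is reported.

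The cost is SAP wording and minor programming, best done before the key break.

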### 9.2 Secondary endpoints:

The secondary endpoints will be as follows:

1) CDRS-R total score response rate, remission rate

2) Change from baseline in CDRS-R subscales and item 13 (suicidal ideation):

The CDRS-R total score will be calculated by adding together the scores for answers to all questions in the 17 items. The subscales are defined as mood, somatic, subjective and behavioral (refer to Appendix 3).

3) Clinical Global Impression of Severity (CGI-S):

Disease severity will be evaluated on the basis of seven grades, from 1 (no disease or abnormality) to 7 (extremely severe disease). The analysis of CGI-S will be based on the score.

### 9.2.1 Analysis of secondary efficacy endpoints

#### 1) Analysis of response rate and remission rate

For each of the indices defined below, the number of responders (number of subjects showing remission) and response rate (remission rate) will be obtained for each treatment group, at weeks 1 to 3, 5, and 6 of administration, and at the final evaluation (week 6 of administration, or at discontinuation of the treatment period), and the Cochran-Mantel-Haenszel test, with stratification by the allocation factor age (<12, ≥12), will be used to compare the duloxetine and placebo groups. In addition, the inter-group difference in response rate (remission rate), and the 95% confidence interval, will be calculated.

Index	Definition
30% response	Reduction of 30% or more in CDRS-R total score compared with baseline
50% response	Reduction of 50% or more in CDRS-R total score compared with baseline
Remission	CDRS-R total score of 28 or less

An analysis with withdrawn subjects taken to be non-responders (non-remission subjects) will also be performed.

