Taking into consideration the potential for a situation in which the mechanism responsible for CDRS-R total score data being missing is “missing not at random”, tipping-point analysis will be performed on the basis of multiple imputation, and the effects of the missing data imputation method on the analysis results will be investigated.

(2) Analysis of secondary efficacy endpoints

The following analyses will be performed with the secondary efficacy endpoints:

1) 30% or 50% response rate, remission rate:

The number of responders and response rate will be obtained for each group, and the Cochran-Mantel-Haenszel test, with stratification by age (<12, ≥12), will be used to compare the duloxetine and placebo groups.

2) CDRS-R subscales and item 13 (suicidal ideation), and CGI-S:

The MMRM method will be used to compare the change from baseline to week 6 of administration in the duloxetine and placebo groups. A linear model with unstructured analysis of covariance of error variance will be applied, using change from baseline as the response variable; treatment groups, observation time-points, and interactions between treatment group and observation point as fixed effects; baseline value, and age (<12 , ≥ 12) as the covariate.

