### 4.3 Target number of subjects

The target number of subjects will be 148 (74 each in the duloxetine and placebo groups).

Rationale for the target sample size:

The number of subjects has been set with reference to the results obtained in two overseas, Phase-3 studies, the HMCL and HMCK studies, with the target population planned for the present study, that is, patients who were aged ≥9 when informed consent was obtained, and ≥7 at initial onset of depressive symptoms. In addition, the number of subjects in the present study has been set with the expectation that more accurate selection of institutions and subjects will enable minimization of the placebo response, and thus increase in the inter-group difference.

In this study, the inter-group difference (placebo - duloxetine) between the duloxetine group and the placebo group in CDRS-R change to week 6 of the treatment period is assumed to be 5.9, the standard deviation in CDRS-R change is assumed to be 12.0 in both groups, and the effect size is predicted to be

0.49. It is thus estimated that 66 subjects per group (total: 132) will be required to achieve a detection power of 80% or higher in a two-sample t-test at a two-sided significance level of 0.05. Therefore, predicting the dropout rate to be 10%, the target total number of subjects has been set at 148 (74 per group).

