### 9.1.1 Primary analysis of primary efficacy endpoint

As the primary analysis, the superiority of duloxetine over placebo will be evaluated in terms of change in CDRS-R total score by week 6 of administration. In detail, all usable data obtained at stipulated time-points after study drug administration will be used, and a linear model (MMRM) will be applied, with change in CDRS-R total score from baseline taken to be a response variable; treatment group, observation time-points, and interaction between treatment group and observation time-points taken to be fixed effects; baseline CDRS-R total score and age (<12, ≥12) taken to be covariates; and an unstructured covariance structure for error variance. In this step, the degree of freedom will be adjusted using the approximation of Kenward and Roger. On the basis of this model, the estimated difference between the duloxetine and placebo groups at week 6 of administration, and its 95% confidence interval, and the p-value, will be calculated.

Examples of SAS codes for applying the above model are shown below.

```
proc mixed data=CDRSR order=internal;
  class SUBJID TRT VISIT AGEGR;
  model CHG=CDRSR_BASE AGEGR TRT VISIT TRT*VISIT / ddfm=kr;
```

```

repeated VISIT / type=un subject=SUBJID;
lsmeans TRT*VISIT;
estimate 'DLX vs PLB' TRT 1 -1 TRT*VISIT 0 0 0 0 1 0 0 0 0 -1 / cl;
run;

```

SUBJID: Subject identification number  
TRT: Group (DLX = duloxetine group; PLB = placebo group)  
VISIT: Stipulated observation time-points (Visits 3, 4, 5, 7 and 8)  
AGEGR: Age category (<12, ≥12)  
CDRSR\_BASE: CDRS-R total score baseline value  
CHG: Change in CDRS-R total score from baseline

If the above model does not converge, a covariance structure will be selected in the following order, and the MMRM method will be applied: (i) heterogeneous AR (1); and (ii) heterogeneous compound symmetry. In addition, time-course graphs of adjusted mean ( $\pm$  standard error) of change in total CERS-R score, estimated by the MMRM method, will be prepared for each treatment group.

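### The age-only CMH test for remission is valid but ignores baseline CDRS-R, which sets how far each child must fall to reach 28; adjusting for it at week 6 would be a cheap, modest gain

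*SAP*

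**What the plan says.** SAP 9.2.1 1) treats 30% response, 50% response and remission alike: "the Cochran-Mantel-Haenszel test, with stratification by the allocation factor age (<12, ≥12), will be used to compare the duloxetine and placebo groups". This is done at weeks 1, 2, 3, 5 and 6 and at the final evaluation, with a between-group difference and 95% CI, and is repeated counting withdrawn subjects as failures. Protocol 8.10.3 (2) has the same test, "with stratification by age (<12, ≥12), will be used to compare the duloxetine and placebo groups". Neither document has a baseline-adjusted analysis of these endpoints.

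The continuous endpoints are handled differently. The primary MMRM (SAP 9.1.1) has "baseline CDRS-R total score and age (<12, ≥12) taken to be covariates". The ANCOVAs (SAP 9.1.2) and the MMRMs for subscales, item 13 and CGI-S (SAP 9.2.1 2)) also adjust for the baseline value, and the subgroup models (SAP 9.1.3) keep baseline while dropping age.

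Allocation is by minimisation on age group and site (SAP 4.2). Entry needs a total of at least 40 with no upper limit (protocol 4.2), and FAS membership needs a baseline total (SAP 5.1).

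**The concern.** Remission is a fixed cut-off, so baseline sets the size of the hurdle. At the entry floor of 40, remission coincides with 30% response; above 56 it is harder than 50% response. A covariate this closely tied to the outcome, recorded for everyone and used elsewhere in the same plan, is left out of the one binary endpoint where it matters most, and no reason is given. Remission is a named secondary objective. At stake are some precision and power, and protection against a chance difference in baseline severity between arms, which the minimisation does not control.

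**Working it through.** **1. The plan's own figure.** The between-group difference "in CDRS-R change to week 6 of the treatment period is assumed to be 5.9" and the "standard deviation in CDRS-R change is assumed to be 12.0 in both groups", with "a detection power of 80% or higher in a two-sample t-test at a two-sided significance level of 0.05".

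- Normal approximation: n = 2 × (1.960 + 0.842)² × (12.0 / 5.9)² ≈ 65 per group.
- Exact t-test: 65.9, so 66 per group, with power 0.8005.
- Dropout: 66 / 0.90 = 73.3, so 74 per group, 148 in total.

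The stated sample size is reproduced. It concerns the primary endpoint only; the documents state no rate or power for remission.

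**2. The hurdle.** Fall needed = baseline − 28.

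| Baseline | Fall to reach 28 | As % of baseline |
|---|---|---|
| 40 | 12 | 30 |
| 50 | 22 | 44 |
| 56 | 28 | 50 |
| 60 | 32 | 53 |
| 70 | 42 | 60 |

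**3. Simulation at the planned evaluable size.** From the documents: 66 per group, difference 5.9, SD of change 12.0, entry floor 40, cut-off 28. Assumed, because the documents are silent: baseline mean and SD (truncated at 40), mean placebo fall, correlation of change with baseline, and 20% aged under 12 with no age effect. There were 3,000 trials per row. The tests compared are CMH by age, and a logistic score test with age and continuous baseline. The last column is the shift in the unadjusted remission difference when baseline means differ by two SDs of their chance variation (about 2.6 to 3.3 points).

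| Baseline mean/SD | Correlation | Placebo fall | Remission %, placebo v duloxetine | CMH power % | Adjusted power % | Gain | Shift (points) |
|---|---|---|---|---|---|---|---|
| 60/10 | 0 | 18 | 18.1 v 30.1 | 36.6 | 44.6 | 8.0 | 6.5 |
| 60/10 | 0 | 24 | 30.4 v 45.0 | 39.8 | 50.2 | 10.4 | 7.8 |
| 60/10 | −0.3 | 18 | 13.9 v 26.5 | 44.1 | 48.8 | 4.7 | 4.4 |
| 60/10 | −0.3 | 24 | 26.8 v 43.7 | 52.8 | 57.9 | 5.1 | 5.7 |
| 60/10 | −0.5 | 18 | 10.2 v 23.1 | 51.2 | 53.6 | 2.4 | 2.8 |
| 60/10 | −0.5 | 24 | 23.5 v 42.7 | 65.1 | 68.3 | 3.2 | 4.4 |
| 55/8 | −0.3 | 20 | 28.1 v 46.5 | 58.6 | 62.5 | 3.9 | 4.0 |

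The largest gains come from zero correlation, where the whole baseline difference carries through to week 6. With no treatment effect (two scenarios), CMH rejected in 4.9% and 5.7% of trials and the adjusted test in 4.4% and 6.0%.

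**4. Simulation at 74 per arm, likelihood-ratio test.** In a typical case (baseline 58/10, slope of change on baseline −0.4, placebo fall 20), power rises from 57% to 62%. Null rejection for this version was 5.8% against 5.2% for CMH, so part of the raw gain is a liberal test. With both tests calibrated to 5%, the gain is about 1 to 8 points, about 4 typically. At a slope of −0.8, where week-6 scores keep little of baseline, a calibrated run gave 74.5% for both.

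**5. Where the adjustment does not help.** For 30% and 50% response, the step 3 simulation gives gains of only about 0 to 4 points. At early visits remission is rare: under assumed falls of 5, 8 and 11 points, about 1, 4 and 10 remissions in the whole trial, and the logistic model gave extreme estimates in about 98%, 63% and 17% of runs.

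**The case against.** The strongest reply is that nothing here is wrong. The CMH test holds its size. Under randomisation the unadjusted difference is unbiased, and its interval already allows for chance imbalance. Stratifying on age follows an allocation factor, and the two documents agree. The endpoint is secondary, with no stated power and no multiplicity control (SAP 6.2), and the primary conclusion comes from a baseline-adjusted MMRM. Baseline CDRS-R is tabulated by arm (SAP 7.2), so an imbalance would be seen. The gain depends on figures absent from the documents, and part of the uncalibrated gain reflects a slightly liberal test.

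All of that stands. It rules out reading the age-only test as invalid or as inflating type I error: imbalance matters given the baseline actually drawn, not on average over randomisations. It does not remove the case for adjustment. Seeing an imbalance in a table does not correct for it, and choosing to adjust after seeing it would be post hoc.

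A reader might also infer that all three binary endpoints, at every visit, should move to logistic regression. The definitions in SAP 9.2.1 do not support that. Response is already scaled to each child's own baseline. At the early visits, with entry at 40 or more, remission may be too rare for the model, whereas CMH stays computable.

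**Conclusion.** The point holds as an efficiency improvement for remission at week 6 and at the final evaluation, not as an error in the plan. Adjusting for baseline should add about 1 to 8 points of power, typically 4 to 5, and close to none if week-6 scores hardly depend on baseline. A two-SD chance imbalance would move the unadjusted remission difference by about 3 to 8 percentage points, against true differences of about 12 to 19 in the same scenarios; the adjusted estimate removes this as far as the model describes the baseline relation. These sizes rest on assumed baseline, placebo-change and correlation values. The omission itself, and the dependence of the hurdle on baseline, come straight from the documents. The primary conclusion is not affected.

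**What to change.** Before key break, in SAP 9.2.1 1), prespecify for remission at week 6 and at the final evaluation a logistic regression with treatment, age group (<12, ≥12) and continuous baseline CDRS-R total. Report the standardised risk difference (each FAS child's predicted probability averaged under each treatment in turn) with its 95% CI. Align protocol 8.10.3 (2), or record the change and its reason in the SAP, as protocol 8.1 requires.

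Keep the age-stratified CMH test as supportive at those two time-points, as the analysis of remission at weeks 1, 2, 3 and 5, and for 30% and 50% response throughout.

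The cost is SAP wording and a few lines of code, with no new data. The downside is one more model parameter and a slightly liberal likelihood-ratio test (about 5 to 6% simulated type I error).
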